6.2.12 Follow-Up Visits 1 and 2 (Week 12 and Week 26)

During Follow-Up Visits 1 and 2 (Duration: ~30 minutes) participants will:

1. Perform a CO breath assessment or provide a urine sample for a cotinine assessment, answer combustible marijuana items, and complete a concomitant medication review.
2. Provide daily smoking rate (timeline follow back [TLFB]).
3. Have weight measured.
4. Complete paper and pencil questionnaires:
 - Adverse Events Form (Open-Ended AEs)
 - Physical Activity (PAR)
5. If a participant reports not smoking (not even a puff of a cigarette) for at least the 7 days prior to the Follow-Up Visit without the aid of NRT, the participant will be asked to provide a 5ml saliva sample used to assess cotinine levels and verify abstinence from smoking.
6. Confirm the 24-hour dietary recall (Week 12 [#4] and Week 26 [#5]) schedule.

6.2.13 fMRI Scan Visits 1 & 2 (~Week -2 and ~Week 7-8)

Participants who are both eligible and elect to participate in the neuroimaging sub-study will complete two neuroimaging sessions: Scan 1 will occur prior to the Baseline Visit (~week -2) and Scan 2 will occur during the final week of nicotine patch therapy (~week 7-8). Prior to each scan, participants will be instructed to fast overnight (beginning at ~10pm) until after the

CONFIDENTIAL

This material is the property of the University of Pennsylvania. Do not disclose or use except as authorized in writing by the study sponsor

completion of their fMRI scanning visit the following day. The fast period does not include a Boost® Nutritional Drink (Vanilla) that will be provided during the scanning visit to standardize prior food intake and remove deprivation to increase sensitivity to changes in food reward. Since participants are asked to fast overnight, all scanning sessions will be scheduled to occur in the morning. However, a scan may be completed in the afternoon at the discretion of the Principal Investigator due to extenuating circumstances. Additionally, participants will be instructed not to consume caffeine for 4 hours prior to the beginning of the visit in order to standardize satiety. Including the 1-hour fMRI scan, scanning visits are expected to last ~3 hours in duration. If a scanner hardware/software malfunction occurs and data is unable to be collected, an fMRI scan(s) may be rescheduled at the discretion of the Principal Investigator.

At both scanning visits participants will:

1. Complete a urine drug screen (at least 30ml [two tablespoons] of urine). The urine drug screen will assess the use of any study-prohibited medications/recreational drugs (See Key Exclusionary Criteria; Alcohol/Drugs). Participants who test positive for any study-prohibited medications/recreational drugs will not be permitted to complete the neuroimaging sub-study and may be deemed ineligible for the main study at the discretion of the Principal Investigator.
2. Self-administer a CLIA-waived urine pregnancy test (female participants only). Participants who believe that they may be pregnant are instructed to discontinue participation in both the neuroimaging sub-study and parent study at this time.
3. Perform a BrAC assessment to control for alcohol consumption.
 - Participants with a BrAC greater than 0.010 will be ineligible to complete the neuroimaging sub-study (may remain in the parent study) unless the Principal Investigator permits the participant to reschedule the neuroimaging scan to another day.
4. Perform a CO breath assessment, answer combustible marijuana items, and complete a concomitant medication review.
5. Self-report smoking behavior over the past 24 hours to control for prior tobacco exposure and provide their daily smoking rate (timeline follow back [TLFB]).
6. Have weight measured.
 - Participants weighing over 300 lbs will be ineligible to complete the neuroimaging sub-study. However, participants may remain enrolled in the main study.
7. **SCAN 2 ONLY:** Provide TN progress and adherence information.
8. **SCAN 2 ONLY:** Complete paper and pencil questionnaires:
 - Side Effect Checklist (SEC)
 - Adverse Events Form (Open-Ended AEs)
9. Complete a magnet safety form.
 - Participants who do not meet the fMRI eligibility criteria will be deemed ineligible for the neuroimaging sub-study. Participants may still participate in the parent study per protocol.
10. Complete a set of abbreviated practice tasks similar to those that will be administered during the fMRI scan, as well as an individualized calibration task to determine the amount of food (i.e. "Food Value Number") that is equivalent to \$0.25 in order to calculate the standard portion size of a participant's preferred snack food (i.e. chips or M&Ms®) that may be earned on a given trial within the in-scanner Food

CONFIDENTIAL

This material is the property of the University of Pennsylvania. Do not disclose or use except as authorized in writing by the study sponsor

Reinforcement/Choice task. Participants will be expected to demonstrate an understanding of the tasks and the response device prior to the fMRI scan.

11. Be provided with a Boost® Nutritional Drink and water.
12. Be escorted to the imaging facility at either the Hospital of the University of Pennsylvania or the Stellar Chance building for the brain-scanning portion of the session.
13. **SCAN 1 ONLY:** Participants will smoke one of their own cigarettes (~30 min. before initiating fMRI) in a designated smoking area outside of the building where the fMRI scanner is located in order to standardize the timing of cigarette exposure for all participants.
14. **SCAN 2 ONLY:** Participants will be instructed to remove their TN patch prior to entering the MRI environment. Participants will be provided with a loose, sealed 7mg (NicoDerm® CQ® - Clear) patch to reapply after exiting the MRI environment.
15. Undergo a 1-hour fMRI scan adhering to the procedures and Table 1 below:

Scanning Protocol/Data Acquisition: MRI is performed in a 1-hour session, which, in our experience, participants tolerate easily without discomfort or excessive motion. Prior to entering the scanning area, an approved MRI Technician or MRI User will review the participant's magnet safety form and will confirm that the participant has removed all metal and/or objects containing magnetic strips from their persons. Once the participant is approved to enter the scanning area, the participant will be placed supine in the scanner, wearing earplugs to muffle noise, and fitted with adjustable foam cushions to limit head motion. If a participant requires corrective lenses for vision, but does not have contact lenses, a set of plastic glasses that are approved for use in an MRI scanner will be provided to him/her. Participants will be provided with an emergency squeeze ball, so that they may interrupt the scan and/or be removed from the scanner if necessary. Head fixation will be assured through a foam-rubber device mounted on the headcoil.

Image acquisition is performed on a 3T Siemens Tim-Trio scanner with a FDA approved head coil. A T1-weighted multi-echo magnetization-prepared, rapid acquisition gradient echo (MPRAGE) structural image is acquired using standard parameters at 1mm resolution. This MPRAGE is used for functional image co-registration and transformation into standard template space. Resting BOLD fMRI will be obtained followed by the three task paradigms.

TABLE 1: fMRI Session	
~Duration (mins.)	Activity
5	Structural Scans (localizer, MPRAGE)
10	Resting State BOLD fMRI
15	Food Reinforcement/Choice ^a
12	Working Memory ^{a,b}
10	Food Cue Reactivity ^a
2	B0 Map ^{*if time permits*}
Total Time in Scanner: ~54 minutes	
^a fMRI tasks will be presented in a fixed order	
^b Stimuli (Form A/B) will be counterbalanced within subject	

Task stimuli will be rear projected to the center of the visual field using a PowerLite® 7300 Video projector system (Epson American, Inc., Long Beach, CA) and viewed through a mirror mounted on the head coil. Participants will use a fiber optic response pad (FORP™ Current Design, Inc., Philadelphia, PA) made of non-ferromagnetic components. This MR-compatible button-box is used to record task responses and reaction times. Pulse and respiration are recorded as an index of physiological arousal during the task and to statistically reduce the effects of physiological noise in the fMRI data.

Resting State fMRI: Whole-brain functional MR images will be acquired while subjects rest with eyes closed over 39 axial, interleaving, 4-mm sections by means of a gradient-echo echo planar imaging sequence (150 volumes; echo time/repetition time, 27/2000 milliseconds; flip angle, 80°; field of view, 220 x 220 mm; image matrix, 64x64).

Task fMRI: BOLD images will be acquired using a whole-brain, single-shot gradient-echo (GE) echo-planar imaging (EPI) sequence with the following parameters: TR/TE=2000/30 ms, flip angle 90°, field of view (FOV)=192 mm, matrix = 96X96, isotropic voxel resolution 2.5 mm, slice

CONFIDENTIAL

This material is the property of the University of Pennsylvania. Do not disclose or use except as authorized in writing by the study sponsor

thickness/gap=2.5/0mm, 38 slices axial-oblique parallel to AC-PC. In ongoing studies we find these parameters produce robust signal in ventral brain regions including ventral striatum and orbital/ventral prefrontal cortex with little distortion or signal loss.

Food Cue Reactivity: The task will present (5 sec) 20 pictures of food rated (at Intake) as most appetizing and 20 pictures of food rated (at Intake) least appetizing, and 20 pictures of a water glass. Participants will be instructed to imagine tasting and eating the pictured food for as long as the food is presented. Order of presentation is randomized and the task consists of 60 events separated by an inter-stimuli interval (fixation point) ranging from 2-11 sec (mean 5.5 sec). As a secondary measure, food craving will be assessed prior to and after completion of the scan. The food craving assessment is the 3-item “desire” subscale of the reliable and valid state version of the Food Craving Questionnaire (FCQ-S). Total task time: ~10 minutes.

Food Reinforcement/Choice: Participants choose between a standard low effort monetary reward and either (on separate trials) a food or monetary reward of higher value and effort. Each trial presents a choice between a standard reward (27 button clicks for \$0.25) or exerting greater effort to earn a larger reward. On half of the trials, larger rewards will be \$0.50 (2 x standard value). In the remaining trials the larger reward will be double the calibrated snack portion (e.g., 20 M&Ms). Effort for more valuable rewards will vary from 27 to 775 responses in 25 log10 steps. Pairs of visual stimuli depicting the two options appear for 4.5 sec followed by a 3-14 sec inter-trial interval. Each pairing is presented twice making 50 trials for each class. Left/right position of stimuli is randomized, as is trial type (monetary vs. food; effort levels). To increase motivation to choose food and monetary reward, participants are told they will complete the work and receive the outcome of 4 randomly selected food and monetary (maximum \$2.00) trials. Total task time: ~15 minutes.

Working Memory: We will use a 12-minute visual N-back task validated for fMRI studies of smokers. A total of 20 fractals (target-foil ratio 1:3) are presented for each condition (i.e., 0-back, 2-back, 3-back), and each condition (60 sec block) is repeated 3 times in pseudo-random block design experiment. Each fractal is displayed for 500ms followed by 2500ms inter stimuli interval. Total task time: ~12 minutes.

16. When all scans are completed, participants will be removed from the MRI scanner and be asked to complete a brief ~5-minute “work” task (i.e. clicking on a target a certain amount of times) based on their selections during the in-scanner Food Reinforcement/Choice task on a laptop computer.
17. Participants will receive the appropriate reward(s) (food and/or monetary) per the post-scan work task, as well as receive compensation for time and travel per the study compensation schedule. At the end of the session, participants will be escorted to the exit of the imaging facility where s/he will be free to leave.

6.3 ***Microbiome Sub-Study***

Participants who are both eligible and elect to participate in the microbiome sub-study will be instructed to collect and return stool samples to the Center at **Week -2 (Baseline Visit)**, **Week 4 (Mid-Tx 3 Visit)**, and **Week 8 (End of Treatment Visit after completing TN treatment)**. Participants will be asked about their consumption of yogurt, probiotics, and prebiotics at **the Baseline Visit, Mid-Tx 3 Visit, and End of Treatment Visit**. Participants will be asked to answer a few questions regarding their antibiotic use over the past 6 months at the **Baseline Visit** as well.

Participants will receive a stool sample collection kit and detailed instructions (written and verbal) about how to complete the collection of their stool sample at the in-Center visit prior to the visit when which they are scheduled to return their sample. Ideally, stool samples will be

CONFIDENTIAL

This material is the property of the University of Pennsylvania. Do not disclose or use except as authorized in writing by the study sponsor

collected and returned to the Center in person within 24 hours (up to ~36 hours is permissible) of the designated visit. If a participant is unable to attend a visit at which a stool sample collection kit is distributed, the stool sample collection kit may be mailed to the participant if deemed appropriate by the Principal Investigator. If a participant is unable to attend a visit at which a stool sample is scheduled to be returned or they are physically unable to provide a stool sample within 24-36 hours of their designated sample-return visit, the participant may return their stool sample to the Center on a date after the designated sample-return visit. The Principal Investigator will determine the window of time that a participant will be permitted to return their stool sample after the designated sample-return visit on a case-by-case basis.

In addition to take-home collection instructions and Stool Sample Collection Form, participants will receive the following supplies in a stool sample collection kit: Stool collection bucket with a lid, a frame into which the bucket fits for collection, a large, sealable gallon bag, cold packs and a bag for ice, small styrofoam cooler, nitrile gloves, absorbent, and a shipping box. Participants will complete each stool sample collection at their residence. Participants will be instructed to place the stool collection bucket in the commode, which allows for separation of urine and feces, and keeps the feces separated from the toilet water. Participants will place a lid on the bucket (labeled with participant ID number and designated time point) and record the date and time of sample collection on the Stool Sample Collection Form. The sealed bucket will then be secured in the large bag with absorbent material. The bagged sample should then be placed in the cooler with several cold packs and/or bags of ice.

If the participant is unable to return their stool sample to the Center in person, a cardboard shipping box may be included in the stool sample collection kit for shipping directly to the CHOP Microbiome Center or CIRNA. To prepare for shipping, the Styrofoam cooler is placed in the cardboard shipping box with a biohazard label for shipping by courier. The participant will then call the courier service for pick-up of the sample for overnight delivery to the CHOP Microbiome Center or CIRNA per a standardized procedure.

Stool samples returned to the CIRNA will be immediately refrigerated and hand delivered within a cooler to the CHOP Microbiome Center by the research staff as soon as possible. Once the stool sample is aliquot for metagenomics analyses, the appropriate amount of sample will be delivered to the Penn Metabolomics Core for metabolomics analyses per a standardized procedure.

6.3.1.1 Metagenomics

Metagenomics will be used to examine changes in the composition of the gut microbiome. Shotgun libraries will be generated from 1 ng of DNA using the NexteraXT kit (Illumina, San Diego, CA). Libraries will be sequenced on the Illumina HiSeq using 2x125 bp chemistry in High Output mode. Extraction blanks and DNA free water will be included to empirically assess environmental and reagent contamination. Laboratory-generated mock communities consisting of DNA from *Vibrio campbellii*, *Cryptococcus diffluens*, and Lambda phage will be included as positive sequencing controls. Bioinformatics analysis will be carried out with the Sunbeam metagenomics analysis pipeline, which [name] and staff helped write (<https://doi.org/10.1101/326363>). Adaptor sequences will be removed from reads using Trimmomatic. Host DNA will be identified by alignment to the human genome (version hg38), and low-complexity sequences will be removed using the Komplexity tool, which is distributed with Sunbeam pipeline. Taxonomic classification will be performed using Kraken and a reference database of bacterial genomes available from NCBI. Sequence reads will be assembled into contigs using the ensemble method in MEGAHIT. The bioinformatics analysis will include taxonomic and gene function abundances for bacteria, fungi, and double stranded

CONFIDENTIAL

This material is the property of the University of Pennsylvania. Do not disclose or use except as authorized in writing by the study sponsor

DNA viruses. For classification of bacterial genes, we will utilize the KEGG reference database, for which the Center maintains an institutional license.

6.3.1.2 Metabolomics

Metabolomics will assess the downstream changes in neuroactive products of gut bacteria. Metabolites will be extracted from stool samples according to well-established, validated methods for tissue-based metabolomics and readied for untargeted LC/MS metabolomics. Reversed-phase C18 chromatography to retain and separate medium polarity to nonpolar metabolites will be performed on a Thermo Scientific Ultimate 3000 UHPLC using a Waters Acuity BEH C18 column (2.1 mm x 150 mm, 1.7 μ m). HILIC chromatography to retain highly polar metabolites, not retained by reversed-phase C18 chromatography, will be performed on the Ultimate 3000 using a Waters Acuity BEH-NH2 column (2.1 mm x 150 mm, 1.7 μ m). The Ultimate 3000 UHPLC will be coupled to a novel Thermo Fisher Scientific Orbitrap ID-X mass spectrometer scanned from 75-1000 Da at a resolution of 70,000. Compound Discoverer (Thermo Fisher Scientific, San Jose, CA) will be used to process the LC/MS metabolomics data to identify metabolites and determine statistical differences between study groups.

CONFIDENTIAL

This material is the property of the University of Pennsylvania. Do not disclose or use except as authorized in writing by the study sponsor

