Smoking cessation-induced changes in the abundance of gut bacteria likely have functional, downstream consequences for dietary intake and smoking abstinence. Gut microbes secrete neurotransmitters and other neuroactive metabolites that regulate reward-seeking behavior by communicating pleasure and satiety to the brain via the vagus nerve. For example, dopamine, serotonin, and gamma-aminobutyric acid (GABA), as well as their precursors (tyrosine, tryptophan, and glutamate, respectively), are secreted by multiple genus. Indeed, the gut is a significant source of these key neurotransmitters that are also active in the brain. The gut microbiome also produces neuroactive metabolites (e.g., indole and short chain fatty acid propionate) that impact appetite by stimulating the production of gut hormones with anorectic functions. Shifts in the abundance of bacteria that produce these neurotransmitters and metabolites likely translate to a reduction in these molecules that are involved in reward and appetite regulation. In turn, reduced reward and appetite regulation may drive the substitution of cigarettes with palatable snack foods, as well as smoking relapse.

Can BAS+ Mitigate the Effects of Gut Microbiome Changes on Dietary Intake and Smoking Relapse? Smoking cessation induced changes in the composition of the gut microbiome along with downstream reductions in neuroactive metabolites involved in reward regulation and appetite control likely result in increased food intake (and ultimately weight gain) and smoking relapse. As such, the gut microbiome may provide a biological basis for the observation that smoking cessation heightens the reinforcing value of snack foods, which predicts subsequent food intake and weight gain. In the context of fewer alternative reinforcers and diminished sensitivity to these reinforcers, there is little to compete with food or cigarettes as a reinforcer. BAS+ focuses on increasing the number of, and pleasure derived from, alternative reinforcers to improve cessation rates, mitigate increases in dietary intake, and lesson PCWG. We will explore whether BAS+ (versus SC) mitigates the effects of gut microbiome changes on dietary intake and smoking abstinence at 12 weeks post TQD.

2 Study Objectives

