2.3 Microbiome Sub-Study

Aim 1: To identify earlier (4-weeks post TQD) and persistent (8-weeks post TQD) smoking cessation associated changes in gut microbiome composition and function.

H1a: Smoking cessation will result in decreases in *Prevotella* and *Bacteroides* species from the *Bacteroidetes* phylum, decreases in β - and γ - *Proteobacteria*, increases in *Clostridium* clusters IV and XIV from the *Firmicutes* phylum, and increases in *Bifidobacteria* and HGC bacteria from the *Actinobacteria* phylum.

H1b. We expect to observe decreases in neurotransmitters implicated in reward (dopamine, serotonin, GABA) as well as their precursors (tyrosine, tryptophan, glutamate), and microbial metabolites involved in appetite regulation (indole and propionate).

Aim 2: To evaluate the relationship between post-cessation changes in the gut microbiome, dietary intake, and smoking abstinence.

H2: Greater post-cessation changes in the gut microbiome will predict increased dietary intake and lower smoking abstinence rates 12 weeks post TQD.

[figure not shown]
Aim 3: To explore whether BAS+ (vs. SC) mitigates the effect of gut microbiome changes on dietary intake and smoking abstinence.

H3: Because BAS+ promotes alternative, non-food sources of reinforcement, BAS+ (vs SC) will mitigate the effects of microbiome changes on dietary intake and smoking abstinence 12 weeks post TQD.

3 Study Design

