6.5.5 Microbiome Variables

Participants who are participating in the microbiome sub-study will be instructed to provide stool samples for metagenomic and metabolomic analysis on **Week -2 (Baseline Visit)**, **Week 4 (Mid-Tx 3 Visit)**, and **Week 8 (End of Treatment Visit after completing TN treatment)**. Changes in gut microbiome composition, as determined by metagenomics, will be derived by comparing the relative abundance of bacteria from baseline to weeks 4 and 8. Changes in neuroactive metabolites, as determined by metabolomics, will be derived by comparing levels from baseline to weeks 4 and 8. Although we have hypotheses involving specific metabolites, we chose an untargeted metabolomics approach to enable the identification of other biomarkers of importance.

CONFIDENTIAL

This material is the property of the University of Pennsylvania. Do not disclose or use except as authorized in writing by the study sponsor

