6.12 Statistical Methods - Microbiome Sub-Study

For **Aim 1, H1a**, the abundance of bacterial taxa will be analyzed at a community level using pairwise distance between samples, and visualized with Principal Coordinates Analysis. That pairwise distance will be the basis for the omnibus tests in all three aims. Prior to the testing of individual taxa, we will conduct a longitudinal MANOVA (Multivariate ANOVA) based on the profile of relative abundances of the gut taxa of interest. P-values from multiple testing procedures will be corrected to control for a specified false discovery rate using the Hochberg method. For **H1b**, we will repeat the omnibus MANOVA test as in H1a using the absolute levels of metabolites, and follow with tests on individual metabolites should the overall test prove significant. Smoking behavior (smoking rate) will be included in the statistical models for Aim 1 as a covariate, because not all participants will have maintained smoking abstinence from TQD through EOT. **Aim 2** will evaluate the impact of post-cessation changes (pre-post changes) in the gut microbiome on dietary intake (kcals, continuous outcome) and smoking cessation (point-prevalence, binary outcome). We will use generalized linear models fitted using Generalized Estimating Equations. We will specify the logistic model for the binary abstinence outcome, and

CONFIDENTIAL

This material is the property of the University of Pennsylvania. Do not disclose or use except as authorized in writing by the study sponsor

Gaussian dietary intake outcome. We will begin the analysis with the effect of the omnibus measure (pre-post distance). Should that prove significant, we will continue on to specific taxa and metabolites. **Aim 3** will explore whether treatment modifies the effect of gut microbiome changes on dietary intake and smoking cessation. We will enter interaction terms (e.g., treatment x microbiome changes) to the models generated for Aim 2. The interactions will be retained if the z-score is significant ($p<0.05$).

7 Risks / Benefits

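### The 75 Da scan start in section 6.3.1.2 excludes the deprotonated ion of propionate (m/z 73.03), which puts the propionate follow-up test of H1b at risk

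*Combined protocol and SAP*

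**What the plan says.** Section 2.3 (H1b) predicts that smoking cessation will lower eight named compounds: three neurotransmitters (dopamine, serotonin, GABA), their three precursors (tyrosine, tryptophan, glutamate), and "microbial metabolites involved in appetite regulation (indole and propionate"). Section 1.3 gives the reasoning for the last pair, citing "indole and short chain fatty acid propionate" as bacterial products that act on appetite through gut hormones.

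Section 6.3.1.2 describes one assay. Stool extracts are "readied for untargeted LC/MS metabolomics", run on a C18 and a HILIC column, with the "mass spectrometer scanned from 75-1000 Da at a resolution of 70,000". A software package "will be used to process the LC/MS metabolomics data to identify metabolites" and to compare groups. The section gives no ion polarity, no derivatisation step, no propionate standard and no separate short-chain fatty acid assay.

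Section 6.5.5 confirms that the choice was deliberate: "Although we have hypotheses involving specific metabolites, we chose an untargeted metabolomics approach", so that other biomarkers could also be found.

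Section 6.12 sets the H1b analysis: "we will repeat the omnibus MANOVA test as in H1a using the absolute levels of metabolites". Tests on individual metabolites follow if the overall test is significant. The section does not list the metabolites that enter the MANOVA, and it has no rule for a hypothesised metabolite that is not detected.

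**The concern.** The scan range and the hypothesis do not match for one compound. Propionate is the lightest of the eight targets, and a carboxylic acid is normally observed by mass spectrometry as its deprotonated ion. For propionate that ion is lighter than anything the instrument is set to record.

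Propionate is a prespecified target and half of the appetite part of H1b. If its main ion is never scanned, it may have no level at all, or a level taken from an ion whose suitability nobody has stated or checked. Because the plan is silent on non-detection, propionate could drop out of H1b without comment, or its absence could be described as no change.

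**Working it through.** **Inputs from the documents.** Scan range 75 to 1000 Da (section 6.3.1.2). Eight compounds (section 2.3, H1b). Propionate is a short-chain fatty acid (section 1.3).

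**Inputs not in the documents.** Molecular formulas; atomic masses C 12.0000, H 1.007825, N 14.003074, O 15.994915; proton 1.00728. These are physical constants. Ions are taken as singly charged, so that m/z and Da can be compared directly.

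The plan gives no figure to reproduce; 75 Da is a setting.

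**Formulas.** M = sum of atomic masses. [M-H]- = M - 1.00728. [M+H]+ = M + 1.00728.

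**Propionic acid, C3H6O2.**
- M = 3(12) + 6(1.007825) + 2(15.994915) = 36 + 6.04695 + 31.98983 = 74.0368
- [M-H]- = 74.0368 - 1.0073 = 73.0295, which is 75 - 73.0295 = 1.97 below the scan start
- [M+H]+ = 74.0368 + 1.0073 = 75.0441, which is 0.044 above it

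**All eight compounds.**

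| Compound | Formula | M | [M-H]- | [M+H]+ |
|---|---|---|---|---|
| Dopamine | C8H11NO2 | 153.079 | 152.072 | 154.086 |
| Serotonin | C10H12N2O | 176.095 | 175.088 | 177.102 |
| GABA | C4H9NO2 | 103.063 | 102.056 | 104.071 |
| Tyrosine | C9H11NO3 | 181.074 | 180.067 | 182.081 |
| Tryptophan | C11H12N2O2 | 204.090 | 203.083 | 205.097 |
| Glutamate (as acid) | C5H9NO4 | 147.053 | 146.046 | 148.060 |
| Indole | C8H7N | 117.058 | 116.051 | 118.065 |
| Propionate (as acid) | C3H6O2 | 74.037 | **73.030** | 75.044 |

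Of these 16 ions, only propionate [M-H]- falls below 75.

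**Other propionate ions inside the range.** [M+NH4]+ 92.071, [M+Na]+ 97.026, formate adduct 119.035, acetate adduct 133.051, and the dimer [2M-H]- at 2(74.0368) - 1.0073 = 147.066.

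**What follows under each possible method.**
- Underivatised, negative mode: the usual ion is outside the scan; only adducts or the dimer remain.
- Underivatised, positive mode: the protonated ion is inside by 0.044; the sodium and ammonium adducts are also inside.
- Derivatised: the ion is heavier and could lie well inside the range, but no such step is described.

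**The case against.** The strongest reply is that the deciding premise is not in the protocol. Section 6.3.1.2 states no polarity. It refers to established extraction methods without giving the chemistry, so derivatisation is neither described nor excluded. That an acid is best seen in negative mode is general chemistry. This stands, and the conclusion is conditional on it.

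A reader might infer that propionate cannot be measured at all, or that H1b cannot be tested. The documents do not support either reading. Several propionate ions fall inside the window, and whether they give a usable signal cannot be settled from the text. The omnibus MANOVA can run on the other seven compounds. Nothing in section 6.12 says that a non-detected compound would be treated as unchanged; the gap is that no rule is given.

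It can also be said that breadth was chosen on purpose (section 6.5.5) and that the matter touches one compound in a sub-study of up to 60 people. Both points are fair and limit the priority. They do not remove the mismatch: a target named in advance has its usual ion outside the only scan described, and the plan does not say which ion or method would replace it.

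**Conclusion.** The point holds in a limited form. A scan starting at 75 Da excludes the underivatised deprotonated ion of propionate. That part is arithmetic and is certain. It affects one of eight H1b compounds and one of its two appetite metabolites.

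The consequence is conditional. Assuming underivatised detection in negative mode, propionate would rest on secondary ions, or on an ion at the scan edge if positive mode is also run, and its follow-up test is at risk of having no value or an unvalidated one. If the core laboratory derivatises short-chain acids, or has validated another ion, the risk may disappear, but the protocol would still need to say so.

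The effect is confined to the microbiome sub-study: the propionate part of H1b, and any propionate test reached under its Aim 2. The parent trial's primary outcomes and sample size are untouched.

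**What to change.** In section 6.3.1.2, do one of the following:

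- lower the start of the scan so that m/z 73.03 is included, at least in negative mode, and confirm detection with a propionate standard; or
- keep the range and name the derivative or alternative ion by which propionate will be quantified.

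State the polarity in either case.

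In section 6.12, add that if propionate proves not measurable it will be reported as not assayed rather than unchanged, and left out of the H1b metabolite tests. If the H1b family is the eight named compounds, this reduces it to seven, so it should be settled before the metabolite results are analysed. If acquisition is already complete, the same statement should be made before analysis.

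The cost is one acquisition setting, one standard and a few lines of text. The downside of a lower scan start is slightly more low-mass background.
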